5.4.1 Treatment assignments

Individuals will be randomized at an allocation of 2:1 experimental to standard of care arm. The experimental group will receive high dose influenza vaccine with a booster high dose flu vaccine one month later. The standard of care group will receive a single influenza vaccine (standard dose if age <65 and high dose if age ≥ 65) and a placebo booster vaccine after one month. All study injections, whether vaccine or placebo will be redrawn into a fresh syringe to assist in blinding. Only the research pharmacist will have a record of the contents of each study injection.

5.4.2 Dosing regimen

The planned vaccine administration for investigation for experimental group is:

- 1) Fluzone® high-dose vaccine after flu vaccines are available (starting August 2015);
- 2) Fluzone® high-dose vaccine as a second booster dose to all subjects in each cohort.

The planned vaccine administration for investigation for standard of care group is:

- 1) Fluzone® high-dose vaccine if age ≥ 65 or standard dose trivalent inactivated influenza vaccine if age <65. Vaccines will be administered based on standard of care practice after flu vaccines are available (starting August 2015);
- 2) Placebo normal saline injection as a second booster dose to all patients in this group.

A Comprehensive Cancer Center Designated
by the National Cancer Institute

Phase: II

YCC Version 4.0 Date: 31-May-2017

pg. 18

5.4.4 Record of administration

Accurate records will be kept of all vaccine administration.

Discontinuation of Study Treatment

Follow up will continue until the last study visit or the occurrence of any of the following events.

- Adverse event(s) that, in the judgment of the Investigator, may cause severe or permanent harm or which rule out continuation of the treatment regimen.
- Withdrawal of consent
- Lost to follow up
- Death

Adverse events

Toxicity will be scored using CTCAE Version 4.0 for toxicity and adverse event reporting. A copy of the CTCAE Version 4.0 can be downloaded from the CTEP homepage (<http://ctep.info.nih.gov>). All appropriate treatment areas should have access to a copy of the CTCAE Version 4.0.

Because any attribution of an adverse event from a vaccine would be expected to occur immediately or within several days, adverse events will only be recorded for a period of 30 days from each study vaccine. Within this time frame, all adverse clinical experiences grade 2 or higher, whether observed by the investigator or reported by the patient, must be recorded, with details about the duration and intensity of each episode, the action taken with respect to the study vaccine, and the patient's outcome.

Following the 30-day window after the booster vaccine, survival data will be collected for the remainder of the influenza season in addition to any influenza-like illnesses and documented influenza infections.

Serious Adverse Event (SAE) Definition

- Results in death
- Is life-threatening¹
- Requires inpatient hospitalization or prolongation of existing hospitalization

A Comprehensive Cancer Center Designated
by the National Cancer Institute

Phase: II

YCC Version 4.0 Date: 31-May-2017

pg. 19

- Results in persistent or significant disability or incapacity²
- Is an important medical event³

¹“Life-threatening” means that the subject was at immediate risk of death at the time of the serious adverse event; it does not refer to a serious adverse event that hypothetically might have caused death if it were more severe.

²“Persistent or significant disability or incapacity” means that there is a substantial disruption of a person’s ability to carry out normal life functions.

³Medical and scientific judgment should be exercised in deciding whether expedited reporting is appropriate in situations where none of the outcomes listed above occurred. Important medical events that may not be immediately life-threatening or result in death or hospitalization but may jeopardize the patient or may require intervention to prevent one of the other outcomes listed in the definition above should also usually be considered serious. Examples of such events include allergic bronchospasm requiring intensive treatment in an emergency room or at home, blood dyscrasias or convulsions that do not result in inpatient hospitalization, or the development of drug dependency or drug abuse. A new diagnosis of cancer during the course of a treatment should be considered as medically important.

Protocol Amendments/Deviations

Protocol amendments

Any amendment to this protocol must be agreed to by the Principal Investigator and IRB.

Protocol deviations

When an emergency occurs that requires a deviation from the protocol for a subject, a deviation will be made only for that subject. A decision will be made as soon as possible to determine whether or not the subject (for whom the deviation from protocol was effected) is to continue in the study. The subject’s medical records will completely describe the deviation from the protocol and state the reasons for such deviation. In addition, the Investigator will notify the IRB/EC in writing of such deviation from protocol per IRB Policy 710.

Non-emergency minor deviations from the protocol will be permitted with approval of the Principal Investigator.

Data Management

Analyses and Reporting

Clinical data will be coded and blinded from the study investigators after randomization. Data will be analyzed and reported after all accrual is completed. All subsequent data collected will be analyzed and reported in a follow-up clinical report.

A Comprehensive Cancer Center Designated
by the National Cancer Institute

Phase: II

YCC Version 4.0 Date: 31-May-2017

pg. 20

Data Monitoring Committee

The study team will monitor the data on a regular basis. There is no formal DMC for this minimal risk study.

The principal investigator is responsible for monitoring the data, assuring protocol compliance, and conducting the safety reviews at the specified frequency [monthly]. During the review process the principal investigator will evaluate whether the study should continue unchanged, require modification/amendment, or close to enrollment.

The principal investigator, the Institutional Review Board (IRB), Yale Cancer Center Data and Safety Monitoring Committee (DSMC) have the authority to stop or suspend the study or require modifications.

This protocol presents minimal risks to the subjects and adverse events or other problems are not anticipated. In the unlikely event that such events occur, Reportable Adverse Events (which are events that are serious or life-threatening and unanticipated (or anticipated but occurring with a greater frequency than expected) and possibly, probably, or definitely related) or unanticipated problems involving risks to subjects or others will be reported in writing to the IRB (using the appropriate forms from the website) and any appropriate funding and regulatory agencies per IRB policy 710. The investigator will apprise fellow investigators and study personnel of all adverse events that occur during the conduct of this research project [via email as they are reviewed by the principal investigator.]

Biostatistical Considerations

The primary endpoint of this randomized Phase II study is a composite measure of two clinical endpoints. A patient is considered a treatment failure if either of the following events occur during the 2015-6 flu season:

- Progression of the underlying plasma cell disorder
- Any documented flu infection

We plan to enroll 50 patients in the standard care group and 100 in the vaccine group for a total of 150. Patients will be separately allocated in this 1:2 ratio based on their disease type of early disease versus active disease in order to maintain balanced stratification between the groups. For each disease type, this 1:2 ratio will be performed in blocks of three in order to maintain balance in the study at all times. A randomization schedule will be prepared by the study biostatistician, [name], in advance of the trial beginning. If the standard care group has 0.70 probability of success (defined above) and the vaccinated group has probability of success equal to 0.90 then the power of this design is 0.93. As another example, if the standard care group has 0.75 probability of success and the vaccinated group has 0.90 probability of success then the power of

A Comprehensive Cancer Center Designated
by the National Cancer Institute

Phase: II

YCC Version 4.0 Date: 31-May-2017

pg. 21

our design is 0.78 at significance level 0.1. Patient deaths which are not related to influenza or disease progression will be censored for efficacy analysis.

Yale University's online OnCore system will be used to randomize the patients. Randomization will be performed by the clinical trials office of Yale University and the information released only to the research pharmacist.

We will monitor the study for the toxicity of the vaccine. The unacceptable toxicities include any serious adverse event grade 3 or higher which is believed to be related to the study vaccine. The tolerability will initially be tested in the first 20 patients in the vaccine arm. We will consider the vaccine tolerable if the rate of vaccine related toxicity is 10% or less and intolerable if 30% or more. If, in the first 20 patients, we observe 5 or more patients with vaccine related toxicity, then the cohort will be terminated early. With this design, the probability of terminating the cohort early is 0.04 if the true but unknown toxicity rate is 10% and 0.76 if the true rate is 30%.

Regulatory Considerations

Institutional Review Board/Ethics Committee approval

The protocol for this study has been designed in accordance with the general ethical principles outlined in the Declaration of Helsinki. The review of this protocol by the IRB/EC and the performance of all aspects of the study, including the methods used for obtaining informed consent, must also be in accordance with principles enunciated in the declaration, as well as ICH Guidelines, Title 21 of the Code of Federal Regulations (CFR), Part 50 Protection of Human Subjects and Part 56 Institutional Review Boards.

Any amendments to the protocol after receipt of IRB/EC approval must be submitted by the Investigator to the IRB/EC for approval. The Investigator is also responsible for notifying the IRB/EC of any serious deviations from the protocol, or anything else that may involve added risk to subjects.

Any advertisements used to recruit subjects for the study must be reviewed and approved by the IRB/EC prior to use.

Informed consent

The Investigator must obtain informed consent of a subject or his/her designee prior to any study related procedures as per GCP as set forth in the CFR and ICH guidelines.

Documentation that informed consent occurred prior to the subject's entry into the study and the informed consent process should be recorded in the subject's source documents. The original

A Comprehensive Cancer Center Designated
by the National Cancer Institute

Phase: II

YCC Version 4.0 Date: 31-May-2017

pg. 22

consent form signed and dated by the subject and by the person consenting the subject prior to the subject's entry into the study, must be maintained in the Investigator's study files.

Subject confidentiality

The principle investigator affirms the subject's right to protection against invasion of privacy.

Study records requirements

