Fluzone is standardized according to United States Public Health Service requirements and is formulated to contain HA of each of the following three influenza strains recommended for the current influenza season, including two A subtypes (H3N2 / H1N1) and one influenza B subtype.

Dosage form

Fluzone® High Dose is supplied in 0.5 mL for intramuscular injection

Adverse events:

In adults 18 through 64 years of age, the most common injection-site reaction was pain (>50%); the most common solicited systemic adverse events were headache and myalgia (>30%).

In adults >65 years of age, the most common injection-site reaction was pain (>20%); the most common solicited systemic adverse events were headache, myalgia, and malaise (>10%).

Post Marketing Experience

The following events have been spontaneously reported during the post-approval use of Fluzone.

- Blood and Lymphatic System Disorders: Thrombocytopenia, lymphadenopathy.
- Immune System Disorders: Anaphylaxis, other allergic/hypersensitivity reactions (including urticaria, angioedema)
- Eye Disorders: Ocular hyperemia

A Comprehensive Cancer Center Designated
by the National Cancer Institute

Phase: II

YCC Version 4.0 Date: 31-May-2017

pg. 16

- Nervous System Disorders: Guillain-Barré syndrome (GBS), convulsions, febrile convulsions, myelitis (including encephalomyelitis and transverse myelitis), facial palsy (Bell's palsy), optic neuritis/neuropathy, brachial neuritis, syncope (shortly after vaccination), dizziness, paresthesia
- Vascular Disorders: Vasculitis, vasodilatation/flushing•
- Respiratory, Thoracic and Mediastinal Disorders: Dyspnea, pharyngitis, rhinitis, cough, wheezing, throat tightness
- Skin and Subcutaneous Tissue Disorders: Stevens-Johnson syndrome
- General Disorders and Administration Site Conditions: Pruritus, asthenia/fatigue, pain in extremities, chest pain
- Gastrointestinal Disorders: Vomiting

Screening and Eligibility

The Investigator is responsible for keeping a record of all subjects who sign an Informed Consent Form for entry into the study. All subjects will be screened for eligibility. Screening procedures are outlined in Section 2, Schedule of Study Assessments and may take place on or < 30 days before the day of first vaccine administration.

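### Recording of all adverse events, serious ones included, stops 30 days after each injection with no check at the May contact, which must be reconciled with the untimed reporting duties elsewhere in the protocol

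*Combined protocol and SAP*

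**What the plan says.** **Recording window.** The Adverse events section (Investigational Plan) states that "adverse events will only be recorded for a period of 30 days from each study vaccine". The reason it gives begins "Because any attribution of an adverse event from a vaccine would be expected to occur immediately or within several days". It makes no exception for serious events. The section that follows defines a serious adverse event, but sets no longer window and no rule for following an event to resolution.

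**Content of the record.** Events of grade 2 or higher inside the window "must be recorded, with details about the duration and intensity of each episode, the action taken with respect to the study vaccine". Outcome is a required item as well.

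**After the window.** The same section says that "survival data will be collected for the remainder of the influenza season in addition to any influenza-like illnesses and documented influenza infections". The Schedule of Study Assessments adds influenza-related hospitalization and death to what is asked at the End of Study contact (1 to 15 May 2016), which may be by telephone or email. The schedule marks adverse event assessment at the second-vaccine and Month 2 visits only.

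**Reporting duties.** The Data Monitoring Committee section (Data Management) requires written IRB reporting of "Reportable Adverse Events (which are events that are serious or life-threatening and unanticipated (or anticipated but occurring with a greater frequency than expected") that are at least possibly related. It also has the investigator tell colleagues and study staff about every adverse event arising while the project runs. Neither duty has an end date.

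**End of follow-up.** Under Discontinuation of Study Treatment, "Follow up will continue until the last study visit or the occurrence of any of the following events". The list includes an adverse event that the investigator judges may cause severe or permanent harm.

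**The concern.** One section closes the adverse event record 30 days after an injection. Another sets duties about adverse events that run for the whole project. Between the closing of the window and the May contact, no procedure asks about or records a serious event unless it is a death or related to influenza. The May contact takes place anyway and already asks about health events.

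There is a second gap for events that begin inside the window. Duration and outcome must be recorded, but an event still open at Month 2 meets no further scheduled assessment. Read literally, the rule on the end of follow-up also allows follow-up to stop at an event that may cause severe or permanent harm, which is where the outcome matters most.

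What is at stake is the completeness of the safety record. The experimental arm receives two high-dose injections irrespective of age, while the protocol gives the product's indication as 65 years and older. There is no formal data monitoring committee, so the principal investigator's monthly safety review depends on what is collected.

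**Working it through.** **The plan's own figure.** The only stated safety figures are the early-termination probabilities in Biostatistical Considerations, for 5 or more toxicities in the first 20 vaccine-arm patients. The exact binomial tail P(X ≥ 5 | n = 20) is 0.0432 at a true rate of 10% and 0.7625 at 30%. These agree with the stated 0.04 and 0.76, and this point does not dispute them.

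**Inputs for the recording period**
- Window: 30 days from each injection (Adverse events).
- Booster: nominally day 30. The earliest is day 23 (−7 days). The latest is day 44 in the synopsis (+14 days) or day 51 in the schedule (+21 days). These two limits contradict each other and must be reconciled.
- First vaccine to end of season: roughly 4 to 8 months (Rationale for Treatment in this Setting), taken here as 4 × 30.5 = 122 to 8 × 30.5 = 244 days.
- Month 2 visit: about 30 days after the second vaccine, +14/−7 days (schedule).

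**Days covered** = min(30, booster day) + 30
- Booster at day 30: 30 + 30 = 60 days.
- Booster at day 23: 23 + 30 = 53 days.
- Booster at day 44 or 51: 30 + 30 = 60 days.

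**Days not covered**, booster at day 30
- 4 months: 122 − 60 = 62 days (60/122 = 49% covered).
- 8 months: 244 − 60 = 184 days (60/244 = 25% covered).

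**Late booster.** The total uncovered stays at 62 to 184 days, but part of it moves between the injections: 44 − 30 = 14 days, or 51 − 30 = 21 days.

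**Last scheduled adverse event check.** Month 2 may fall on day 30 − 7 = 23 after the booster. The final 7 days of the window then have no later scheduled inquiry.

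**Could merged visits close the gap?** A schedule footnote lets the Month 2 and End of Study visits merge if they fall within 15 days of each other. Even with the latest booster, the latest Month 2 visit and the shortest stated follow-up, Month 2 falls on day 51 + 30 + 14 = 95. That leaves 122 − 95 = 27 days, so merging does not apply within the stated 4 to 8 months.

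**Sections side by side**
- *Recording against reporting.* Recording ends at 30 days, while IRB reporting and staff notification have no end. After the window the duties can be met only if the investigator happens to learn of an event.
- *Outcome against schedule.* Outcome and duration are required, but no assessment after Month 2 can supply them for an open event.
- *Outcome against end of follow-up.* Outcome is required, yet a severe event is listed among those that end follow-up.

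**The case against.** The strongest reply is that the window is stated, reasoned and wide compared with the onset that the protocol expects. The vaccine is licensed, the study is classed as minimal risk, and the pilot reported no related event of grade 2 or higher in 51 patients. Safety is neither a primary nor a secondary endpoint. Ending routine recording does not stop an investigator from reporting an event that comes to light, so the IRB duty can still be met. The requirement to record outcome can also be read as covering any event that starts in the window, with no date by which the outcome must be known.

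Much of this stands. It rules out several stronger readings that a reader might infer:

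- *That the protocol lists late-onset risks which the window will miss.* Post Marketing Experience names "Nervous System Disorders: Guillain-Barré syndrome (GBS), convulsions, febrile convulsions, myelitis", and also optic neuritis, brachial neuritis and vasculitis. It gives no onset time for any of these. Any percentage of missed events would rest on an assumed onset curve.
- *That late serious events vanish from the data and cannot reach the IRB.* Deaths and influenza-related hospitalizations are collected to the end of the season, and spontaneous reports have an untimed route.
- *That the stopping rule loses power.* The documents give no fraction of toxicities captured, so no such loss can be shown.
- *That every patient is reached in May.* Withdrawal, loss to follow-up, death and the severe-event rule all end follow-up earlier.

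The reply does not remove the inconsistency. The untimed route is passive. It covers only serious related events that are unanticipated or more frequent than expected, so a listed event at its expected frequency falls outside it. The outcome requirement still has no scheduled contact behind it.

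**Conclusion.** The point holds as a gap in ascertainment and an inconsistency between sections. Adverse events, serious ones included, are not actively solicited or recorded for roughly 62 to 184 days of follow-up. This assumes a booster at day 30, months of 30.5 days, and the protocol's 4 to 8 months to the end of the season as a stand-in for the time to the May contact. Length of gap is not the same as risk: how many related events fall in it is unknown and may be none.

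The gap for events open at Month 2, and the mismatch between the recording window and the untimed duties, do not depend on any assumption about onset. This does not undermine the primary analysis. It is a modest weakness in safety capture that is cheap to correct.

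**What to change.** 1. Keep the 30-day window for non-serious events of grade 2 or higher.
2. In the Adverse events section, add that serious adverse events considered possibly, probably or definitely related are recorded through the End of Study contact. This uses the relatedness terms already in the Data Monitoring Committee section and brings the two sections into line.
3. State that events open at Month 2 are followed to resolution or to End of Study, whichever comes first. Reconcile this with the list of events that end follow-up.
4. Add one question on serious adverse events to the May contact, with a matching mark in the schedule limited to these items. The question also covers the last days of the window when Month 2 falls early.
5. Reconcile the two booster windows, and say whether days between injections beyond day 30 are covered.

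The cost is protocol wording and one question at a contact that already takes place. Some unrelated late hospitalizations will have to be screened for relatedness.

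The version reviewed is dated 31 May 2017, after the May 2016 contact. If follow-up is complete, new wording cannot add data. The report should then state that routine adverse event recording ended 30 days after each injection, and limit its safety statements accordingly.

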	Day of Initial Vaccine (Fluzone High Dose in experimental group A vs. standard of care in group B) Day of Initial vaccine, study enrollment and randomization into experimental versus standard of care arm	Day 7 (+/- 2 days) Research blood draw only*	Day of Second Vaccine (Fluzone High Dose in experimental group A vs. placebo booster in group B) Roughly 30 Days following Initial vaccine (+21 days/- 7 days)	Month 2 Roughly 30 Days following Second Vaccine (+14 days/- 7 days)	End of Study Visit ⁴ (may be conducted in person, by telephone, or by email) (End of flu season-May 1 to May 15, 2016)
SPEP OR IFE OR serum free light chains OR quantitative immunoglobulins ¹	X				X
Research blood draw ²	X	*X (patients may refuse this blood draw if it creates an unacceptable burden)	X	*X (if patients are unable to receive this blood draw within the above timeframe, blood draw may be delayed up to 90 days)	*X (patients may refuse this blood draw if it creates an unacceptable burden)
Inquire and document any influenza infection ³ , influenza-related hospitalization, or death during the study period	X		X	X	X
Assessment of all grade II and above adverse events ⁵			X	X	
Pregnancy test for women of childbearing potential ⁶	X		X		

¹ Assessment of disease status within 30 days prior to first vaccine and within 90 days of the End of Study Visit. Both patients with measurable or evaluable disease are eligible. The preferred method to monitor disease should be established at baseline and repeated at the end of study visit. For patients with measurable disease, SPEP or FLC are preferred.

² See Appendix A for details regarding collection of research samples and correlative studies.

³ All subjects should be informed and reminded to present to a health care facility at the first symptoms of possible influenza infection to have DFA checked.

⁴ End of treatment and 30 days following second vaccine may be merged into a single visit if they fall within 15 days of each other.

⁵ See Adverse Events section of the protocol for details.

⁶ Childbearing potential is defined as a sexually mature woman who 1) has not undergone a hysterectomy or bilateral oophorectomy and 2) has not been post menopause for at least 24 months. Pregnancy test to be performed within 2 weeks prior to each vaccine.

A Comprehensive Cancer Center Designated
by the National Cancer Institute

Phase: II

YCC Version 4.0 Date: 31-May-2017

pg. 11

Background and Rationale

Introduction

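### No adverse-event inquiry is scheduled in the days after either injection, so short-lived grade 2 reactions are likely to be under-recorded

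*Combined protocol and SAP*

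**What the plan says.** The Adverse events section of the Investigational Plan explains its recording window as follows: "Because any attribution of an adverse event from a vaccine would be expected to occur immediately or within several days". It concludes that "adverse events will only be recorded for a period of 30 days from each study vaccine". Inside that window, "all adverse clinical experiences grade 2 or higher, whether observed by the investigator or reported by the patient, must be recorded", together with how long each episode lasted, how intense it was, what was done and how it ended.

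In the Schedule of Study Assessments, the row "Assessment of all grade II and above adverse events" is marked in two columns only: the second-vaccine visit and Month 2. It is blank on the first-injection day, at Day 7 and at End of Study. The Day 7 column is headed "Day 7 (+/- 2 days) Research blood draw only", and the blood-draw row adds that "patients may refuse this blood draw if it creates an unacceptable burden". The row's footnote refers to the Adverse events section, which adds no earlier contact. The documents describe no diary, telephone call, solicited-reaction form or observation period after injection. The schedule does accept telephone or email for the End of Study visit.

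**The concern.** The protocol states when it expects attributable reactions, and its scheduled inquiries fall outside that period. The product information in the Study vaccine description lists the kind of reaction at issue: at 18 to 64 years, injection-site pain in more than 50% and headache and myalgia in more than 30%, not split by grade. Such reactions can be over within days. Their grade, onset and duration would then have to be reconstructed at a visit three or more weeks later.

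Dose 2 matters most. At every age it is high-dose vaccine in one arm and saline in the other, given blind, so it is the trial's only randomized contrast of booster reactogenicity. Prior data on the two-dose strategy come only from a single-arm pilot of 51 patients. A grade 2 or higher rate that is too low would read as reassurance about a schedule for which little else is known.

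**Working it through.** **Inputs.** Second-vaccine visit: 30 days after dose 1, +21/-7 days (Schedule of Study Assessments), or +14/-7 days (Study Design table in the synopsis). Month 2: 30 days after dose 2, +14/-7 days (Schedule). Day 7: ±2 days (Schedule). Recording window: 30 days per dose (Adverse events). Stopping rule: 5 or more of the first 20 vaccine-arm patients (Biostatistical Considerations).

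**1. The plan's own safety figure.** The plan gives no figure for completeness of adverse-event capture. Its one safety calculation is the stopping rule. The exact binomial tail P(X ≥ 5), n = 20, is 0.0432 at a true rate of 10% and 0.7625 at 30%. The stated 0.04 and 0.76 are reproduced.

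**2. Time from injection to first scheduled inquiry about the following days.**

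| Dose | Earliest | Latest | Weeks |
|---|---|---|---|
| 1, Schedule window | 30 - 7 = day 23 | 30 + 21 = day 51 | 3.3 to 7.3 |
| 1, synopsis window | 30 - 7 = day 23 | 30 + 14 = day 44 | 3.3 to 6.3 |
| 2 | 30 - 7 = day 23 | 30 + 14 = day 44 | 3.3 to 6.3 |

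The protocol does not define its period of several days. If it is taken as up to 7 days (an assumption), the gap from the end of that period to the inquiry is 23 - 7 = 16 days at least. At most it is 51 - 7 = 44 days for dose 1 (44 - 7 = 37 under the synopsis window) and 37 days for dose 2.

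**3. Against the 30-day window.** The inquiry can fall 51 - 30 = 21 days after the window closes for dose 1 under the Schedule, or 44 - 30 = 14 days after it for dose 2.

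**4. Effect on the dose 2 contrast.** Let the true grade 2 or higher rates be p_V (vaccine) and p_S (saline), and let a fraction r of events be recorded in both arms. The recorded difference is r × (p_V - p_S), so it shrinks in proportion to r. The documents give none of these three quantities. As an illustration by assumption only, with p_V = 15% and p_S = 5%, the true 10-point difference is recorded as 8 points at r = 0.8 and 5 points at r = 0.5. This shows the direction of the error and does not estimate its size.

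**The case against.** The case on the other side has real substance.

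- **Spontaneous reports count.** The protocol requires patient-reported events to be recorded, and a patient may mention one at the Day 7 draw. A reader might infer that under-recording is certain. It is not; it is likely, because nothing prompts the patient during the period when reactions are expected.
- **The quoted sentence justifies a cap on recording and promises no early inquiry.** That is correct. The mismatch is between the stated timing of reactions and the timing of the questions; no commitment is broken.
- **The stopping rule.** A reader might infer that late inquiry disables it. If only 80% or 50% of qualifying events were recorded, the stopping probability at a true 30% rate would fall from 0.76 to 0.54 or 0.17 (the same tail at rates 0.24 and 0.15). The documents do not support that reading: the rule counts related serious events of grade 3 or higher, which depend far less on recall.
- **Endpoints.** The primary endpoint is influenza infection plus progression, and the listed secondary endpoints are antibody titers and T-cell measures. No comparison of adverse events between arms is specified, so no planned efficacy analysis is affected.
- **The second-injection day is not blank.** An assessment is marked there. The documents do not say whether it precedes or follows the injection. If it follows, it could catch an immediate reaction to dose 2, but not one in the next few days.
- **The strategy is not unstudied.** All 51 pilot patients received both doses, with no related grade 2 or higher event. A reader might set 0 of 51 (one-sided 95% upper limit 1 - 0.05^(1/51) = 5.7%) beside the product rates as proof of under-recording. It is not proof: the product rates are not split by grade, and the pilot's method of collecting events is not described.

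**Conclusion.** The point stands as a weakness in the collection of safety data that the protocol itself requires. The first scheduled question about the days after injection comes 3.3 to 7.3 weeks after dose 1 (3.3 to 6.3 under the synopsis window) and 3.3 to 6.3 weeks after dose 2. Seven weeks therefore applies only to dose 1, and only under the Schedule's window.

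Short-lived grade 2 reactions that patients do not volunteer are likely to be under-recorded or misgraded. If recall is similar in both arms, any observed vaccine-versus-saline difference after dose 2 would be too small. That conclusion rests on two assumptions: that some transient reactions go unreported without a prompt, and that recall over weeks is imperfect. How much is lost cannot be derived from the documents. The remedy is inexpensive and should be adopted, but the gap gives no reason to doubt the efficacy design.

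**What to change.** 1. Mark the adverse-event row in the existing Day 7 column. Ask at the draw, or by telephone or email if the draw is declined. With the ±2-day window this falls on days 5 to 9 after dose 1.
2. Add one telephone or email adverse-event inquiry about 7 days after the second injection.
3. Keep the two later inquiries for the remainder of the 30-day windows.
4. State whether the assessment on the second-injection day is made before or after the injection.
5. Reconcile the two second-vaccine windows (synopsis +14 days, Schedule +21 days).

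**Cost:** an amendment to the schedule table and at most 150 × 2 = 300 short contacts by existing staff. The number is lower to the extent that patients attend the Day 7 draw. No visit or procedure is added.

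This version is dated 31 May 2017, after the end-of-study window of 1 to 15 May 2016. If collection is complete, report the late inquiry as a limitation on the grade 2 or higher rates and on any comparison between arms after dose 2, and carry items 1 to 3 into the larger studies that this trial is meant to inform.
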